6.1.1 Statistical Analysis

All analyses will be performed by QST using SAS® Version 9.3 or later. All summary tables and data listings will be prepared utilizing SAS® software.

The standard operating procedures (SOPs) of QST will be followed in the creation and quality control of all data displays and analyses.

6.1.2 Baseline Definition

Baseline is defined as the last non-missing assessment prior to first dose of study drug.

6.1.3 Visit Windowing

Data will be summarized based on nominal visit indications with the exception of data captured at early termination and unscheduled visits. Data from early termination and unscheduled visits will be summarized based on mapped visit values. The analysis windows for early termination and unscheduled visits are presented in the following table.

Analysis Windows for Efficacy and Safety Assessments

Scheduled Visit	Target Study Day	Window (Days)
Week 2	15	13 to 17
Week 6	43	40 to 46
Week 8	57	54 to 60
Week 10	71	68 to 74
Week 12	85	82 to 88
Week 14	99	92 to 106

Data collected at early termination and unscheduled visits prior to study day 13 will not be analyzed, with the exception of those identified as Baseline values. Data collected at early termination and unscheduled visits after study day 106 will not be included in analyses.

The definition for the study day included in each study window is defined as below:

Study Day Prior to Day 1 = Visit Date – Baseline Date

Study Day On or After Day 1 = Visit Date - Baseline Date + 1.

If an assessment's mapped visit is a visit at which the subject has data from a scheduled visit present, or if no analyses are planned for the assessment at the mapped visit, or if the data maps to a time period not covered by windowing, the data collected at the early termination or unscheduled visit will not be included in analyses.

In the event of multiple values from unscheduled or early termination assessments within an analysis window, the value closest to the scheduled visit target study day will be used for analyses (assuming there were no results from the scheduled visit present). If two values tie as closest to the time point (for example, one value is before and the other value is after the time point), then the later value will be selected.

Data collected at all visits will be included in the data listings with visit presented as reported by the site.

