Measure and Map BCCs	X	X	X	X	X	X	X	
Determine Clinical Tumor Type	X							
2mm Punch or Shave Biopsy	X							
End of Treatment Excision							Xh	
BCC Imaging ^I	X	X	X	X	X	X	X	

PellePharm, Inc.

Dose Escalating in Sporadic Basal Cell Carcinomas

Systemic Symptoms		X	X	X	X	X	X	
Patidegib /Vehicle Applications ^J		X	X	X	X	X		
Study drug review/Instructions Dispensation ^J		X	Х	х	х	Х		
Concomitant Medications	X	X	X	X	X	X	X	
Adverse Events	X	X	X	X	X	Х	X	
Review Test Article Compliance/Accountability		X	х	Х	Х	Х	Х	
Clinical Evaluation of Surgical Site(s)								X

BCC= basal cell carcinoma; ET = early termination; ISGTA = investigator static global tumor assessment;

- a for subjects who discontinue early during the treatment period, all procedures outlined for the ET visit should be completed at the time of discontinuation.
- b Must be signed prior to any study procedures.
- ^c Medical history will be updated at Baseline visit.
- d Height will be measured at Baseline only.
- ^e Blood samples for laboratory tests will be collected at Screening. Clinically significant laboratory findings at Week 6 or Week 12 will be repeated at the discretion of the Investigator, and the subject will be followed until resolution (return to normal or to the baseline state) or until clinically stable as determined by the Investigator.
- f Week 6 and 12 serums to be done only for women of child bearing potential
- 8 Only to be done for women of child bearing potential
- h Must be within 48 hours of the Week 12 visit.
- ¹ Imaging requirements are provided in the imaging manual.
- Jubjects will be trained on how to administer the study drug at the Baseline visit and retrained at subsequent visits, if necessary. The study drug may be applied at the study visit. Subjects will record any missed doses and provide to the study site for review

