9.1.4 Week 12 (Day 85 ± 3 Days) / Early Termination

The following procedures will be conducted at this visit:

- 1. Record changes in any concomitant medications since the previous visit in the eCRF. Check for prior and concomitant therapies as per Section 7.4.
- 2. Record any new AEs reported spontaneously by the subject or changes in any ongoing AEs. Record subject weight.
- 3. Perform a brief physical exam including vital signs and weight.
- 4. Collect blood samples for routine laboratory analysis (CBC/Diff and serum chemistry).
- 5. The Investigator or designee will assess the treated areas by observations and questioning the subjects as necessary for the signs and symptoms of irritation including pain/burning, pruritus, erythema, edema, and scabbing/crusting.
- 6. The treatment site(s) will be excised.
- 7. The Investigator will question the subject about any concurrent illness or systemic sign or symptom including but not limited to fatigue, loss or change in taste, nausea,

PellePharm, Inc.

Dose Escalating in Sporadic Basal Cell Carcinomas

vomiting, diarrhea, muscle spasms or cramps, changes in quality or quantity of hair in treated areas and any change in frequency of shaving.

- 8. The Study Coordinator or designee will collect and weigh the previously dispensed study drug tube.
- 9. Any missed doses or deviations should be reported.
- 10. Exit the subject from the study and complete the end of study eCRFs.

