5.1.1 Primary Efficacy Endpoint

The primary efficacy endpoint is change in GLI1 mRNA levels in drug-treated versus vehicle-treated tumors at Week 12.

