6.4 Data Sets Analyzed

6.4.1 Intent-to-Treat (ITT) Population

All subjects who are randomized and dispensed study drug will be included in the ITT analysis set. Subjects will be analyzed according to the treatment group they were randomized. All efficacy analyses will be presented using the ITT population and the Per Protocol population.

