6.7.1 Primary Efficacy Analysis

The primary endpoint of change in GLI1 mRNA levels will be evaluated with an analysis of covariance (ANCOVA) with treatment group as factor and baseline value as covariate. Analysis is on a by tumor level. Pairwise comparisons as well as any treated (combining all patidegib groups) versus vehicle will be performed using contrasts within the ANCOVA.

Additionally, if number of results is sufficient, a t-test will be done to perform pairwise comparisons of change in GLI1 mRNA levels of each treatment group with vehicle (and combined patidegib versus vehicle). If assumptions required for a t-test are not met, then a Mann Whitney U test will be performed.

Data will be summarized by visit. Both change from baseline and percent change from baseline will be presented.

This analysis will be done for 2 regions (1) BCC and (2) BCC + tumor-associated stroma.

No imputation on GLI1 data will be performed.

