Asian	xx (xx.x%)	xx (xx.x%)	xx (xx.x%)	xx (xx.x%)	xx (xx.x%)
Black or African American	xx (xx.x%)	xx (xx.x%)	xx (xx.x%)	xx (xx.x%)	xx (xx.x%)
Native Hawaiian or Other Pacific	xx (xx.x%)	xx (xx.x%)	xx (xx.x%)	xx (xx.x%)	xx (xx.x%)
Islander					
White	xx (xx.x%)	xx (xx.x%)	xx (xx.x%)	xx (xx.x%)	xx (xx.x%)
Multiple/Other ^a	xx (xx.x%)	xx (xx.x%)	xx (xx.x%)	xx (xx.x%)	xx (xx.x%)

^a See Listing xx for a complete list of all other races.

SOURCE: USERNAME\SPONSOR\PROJECT\JOBNAME (DATE,TIME)

Table 14.1.1.1: Summary of Subject Demographics and Baseline Characteristics (Intent-to-Treat Population)
(Page 2 of 2)

	Patidegib Gel 2% QD (N=xx)	Patidegib Gel 2% BID (N=xx)	Patidegib Gel 4% QD (N=xx)	Patidegib Gel 4% BID (N=xx)	Vehicle Gel (N=xx)
Height (cm)					
n	XX	XX	XX	XX	XX
Mean	XX.X	XX.X	XX.X	XX.X	XX.X
SD	XX.XX	XX.XX	XX.XX	XX.XX	XX.XX
Median	XX.X	XX.X	XX.X	XX.X	XX.X
Min. to Max.	xx to xx	xx to xx	xx to xx	xx to xx	xx to xx
Weight (kg)					
n	XX	XX	XX	XX	XX
Mean	XX.X	XX.X	XX.X	XX.X	XX.X
SD	XX.XX	XX,XX	XX,XX	XX.XX	XX.XX
Median	XX.X	XX.X	XX.X	XX.X	XX.X
Min. to Max.	xx to xx	xx to xx	xx to xx	xx to xx	xx to xx

^a See Listing xx for a complete list of all other races.

SOURCE: USERNAME\SPONSOR\PROJECT\JOBNAME (DATE,TIME)

Table 14.2.1.1: Analysis of the Primary Efficacy Endpoint: Percent Change in GLI1 mRNA Levels at Week 12 (Intent-to-Treat Population)

	Patidegib Gel 2% QD	Patidegib Gel 2% BID	Patidegib Gel 4% QD	Patidegib Gel 4% BID	Vehicle Gel
	(N=xx)	(N=xx)	(N=xx)	(N=xx)	(N=xx)
1: BCC region H-Score	$(11 - \Lambda \Lambda)$	$\frac{(11-\lambda \Lambda)}{2}$	$\frac{(11-\Lambda\Lambda)}{2}$	$\frac{(1 \cdot \Lambda \Lambda)}{(1 \cdot \Lambda \Lambda)}$	$\frac{(11-\lambda\lambda)}{2}$
Baseline					
Number of tumors	XX	XX	XX	XX	XX
Mean	XX.X	XX.X	XX.X	XX.X	XX.X
SD	XX.XX	XX.XX	XX.XX	XX.XX	XX.XX
Median	XX.X	XX.X	XX.X	XX.X	XX.X
Min. to Max.	xx to xx	xx to xx	xx to xx	xx to xx	xx to xx
Week 12					
Number of tumors	XX	XX	XX	XX	XX
Mean	XX.X	XX.X	XX.X	XX.X	XX.X
SD	XX.XX	XX.XX	XX,XX	XX.XX	XX.XX
Median	XX.X	XX.X	XX.X	XX.X	XX.X
Min. to Max.	xx to xx	xx to xx	xx to xx	xx to xx	xx to xx
Change from Baseline ^a					
Number of tumors	XX	XX	XX	XX	XX
Mean	XX.X	XX.X	XX.X	XX.X	XX.X
SD	XX.XX	XX.XX	XX.XX	XX.XX	XX.XX
Median	XX.X	XX.X	XX.X	XX.X	XX.X
Min. to Max.	xx to xx	xx to xx	xx to xx	xx to xx	xx to xx
Percent Change from Baseline ^a					
Number of tumors	XX	XX	XX	XX	XX
Mean	XX.X	XX.X	XX.X	XX.X	XX.X
SD	XX.XX	XX.XX	XX.XX	XX.XX	XX.XX
Median	XX.X	XX.X	XX.X	XX.X	XX.X

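### GLI1 tissue excised at early termination before Day 82 never reaches the primary analysis, so the analysis labelled ITT is a Week 12 observed-case analysis

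*SAP*

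**What the plan says.** **Tissue collection.** Protocol 9.1.4 covers Week 12 and early termination as one visit, and its step 6 reads "The treatment site(s) will be excised". Footnote a to Protocol Table 1 states that "for subjects who discontinue early during the treatment period, all procedures outlined for the ET visit should be completed at the time of discontinuation". So the plan foresees excision tissue before Week 12 from subjects who leave early.

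**Endpoint.** SAP 5.1.1 says: "The primary efficacy endpoint is change in GLI1 mRNA levels in drug-treated versus vehicle-treated tumors at Week 12". The shell of Table 14.2.1.1 has rows for Baseline and Week 12 only.

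**Visit assignment.** SAP 6.1.3 keeps scheduled visits under their nominal label but places ET and unscheduled data in windows by study day. It leaves such data out of the analyses if they come before Day 13, if they fall between windows, or "if no analyses are planned for the assessment at the mapped visit".

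**Missing data.** SAP 6.7.1: "No imputation on GLI1 data will be performed". SAP 6.1 and Protocol section 10 say the same for the primary endpoint.

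**Populations.** SAP 6.4.1: "All efficacy analyses will be presented using the ITT population and the Per Protocol population". SAP 6.4.3 makes absence from Week 12 a ground for exclusion from Per Protocol. It then retains subjects who leave because of a treatment-related adverse event or a documented lack of effect.

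**The concern.** Taken together, these rules discard primary-endpoint tissue that the protocol asks sites to collect. A subject may have a paired biopsy and excision, belong to the ITT population, and still contribute nothing to the ITT analysis of GLI1.

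The loss need not be random. Protocol 6.3 lists lack of efficacy, disease progression and adverse events among the reasons for leaving, dropouts are not replaced, and each regimen has only six active subjects. The investigator-measured diameter is treated differently, because its last usable on-therapy value is carried forward. Early stoppers can thus stay in that secondary analysis while they vanish from the primary one.

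Showing ITT beside Per Protocol would normally give some idea of how dropout affects the result. For GLI1 it cannot. Even the discontinuers whom SAP 6.4.3 deliberately keeps in Per Protocol have no GLI1 value in either set if they leave before Day 82.

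**Working it through.** **Plan figures reproduced.** Four cohorts of 6 active and 3 vehicle (SAP 4.1) give 4 × (6 + 3) = 36 subjects: 24 active and 4 × 3 = 12 vehicle, with vehicle pooled (SAP 6.1). The SAP windows match the protocol's visit days and tolerances: 15 ± 2; 43, 57, 71 and 85 ± 3; 99 ± 7.

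**What happens to a GLI1 sample taken at an ET visit, by study day (SAP 6.1.3):**

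| Study days | Number of days | Outcome |
|---|---|---|
| 1–12 | 12 | Dropped: before Day 13 |
| 18–39, 47–53, 61–67, 75–81 | 22 + 7 + 7 + 7 = 43 | Dropped: between windows |
| 13–17, 40–46, 54–60, 68–74 | 5 + 7 + 7 + 7 = 26 | Dropped: maps to Week 2, 6, 8 or 10, with no GLI1 analysis |
| 82–88 | 7 | Used as Week 12 |

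For Days 1–81, 12 + 43 + 26 = 81, so on 0 of 81 days does the sample enter the analysis. With no imputation it cannot return by another route.

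**Texts that might rescue the sample.** SAP 6.7.1 says the data are summarized by visit, which could at most add a descriptive row. The note to Table 14.2.1.1 on summarizing available data belongs to a Baseline and Week 12 shell and does not override 6.1.3. The general carry-forward sentence in Protocol 10.8.5 conflicts with the explicit rule of no imputation for the primary endpoint.

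**Precision.** Assume one tumor per subject, equal variances and simple pooling for the combined contrast. The SE is then proportional to √(1/n_active + 1/n_vehicle), with 12 vehicle subjects throughout.

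- One regimen, no loss: √(1/6 + 1/12) = 0.500
- One lost: √(1/5 + 1/12) = 0.532, ratio 1.065 (+6.5%)
- Two lost: √(1/4 + 1/12) = 0.577, ratio 1.155 (+15.5%)
- All patidegib, no loss: √(1/24 + 1/12) = 0.3536
- One lost: √(1/23 + 1/12) = 0.3561, ratio 1.007 (+0.7%)
- Two lost: √(1/22 + 1/12) = 0.3589, ratio 1.015 (+1.5%)

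**How often.** The documents give no dropout rate. The figures below assume independent early termination before Day 82 at rate d. The chance that a given arm of 6 loses at least one subject is 1 − (1 − d)^6.

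| Assumed d | Expected losses of 36 | Arm of 6 loses at least one |
|---|---|---|
| 5% | 1.8 | 26% |
| 10% | 3.6 | 47% |
| 20% | 7.2 | 74% |

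These are upper limits on what ET tissue could restore, because some early stoppers will have none.

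**The case against.** The strongest reply is that the exclusion follows from the endpoint. GLI1 change is defined at Week 12, and both documents refuse imputation for it. Letting a sample from a few days of treatment stand for the endpoint would change the question and act much like carrying a value forward. This stands as an argument against replacing the Week 12 analysis. It does not argue against a second analysis shown beside it.

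Other points limit the concern:

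- **Tissue is not assured.** Protocol 5.1 asks early stoppers to complete Week 12 assessments as appropriate and if possible. Protocol 6.3 lifts protocol follow-up after disease progression or a switch of treatment. A reader might infer that tissue exists for every dropout; the documents do not support that.
- **The quoted clause is only part of the mechanism.** It decides 26 of the 81 days. A reader might infer that wider windows could never help. In fact a Week 12 window opening at Day 78, midway between Days 71 and 85, would admit Days 78–81. It would not help a sample from, say, Day 43.
- **ITT and Per Protocol are not the same set.** It is tempting to say that Per Protocol simply requires Week 12 attendance and so repeats the ITT exclusion. SAP 6.4.3 retains some discontinuers, and it also removes subjects for eligibility, compliance, interfering medication, insufficient BCC and mismeasured tumors. What holds is narrower: the comparison carries no information about dropout for GLI1.
- **The values are not hidden.** SAP 6.1.3 sends data from all visits to the listings, and Listing 16.2.6.2 shows each H-score with its visit and date.
- **Inference is descriptive.** SAP 6.1 plans no formal testing, and no power is claimed. This lowers the stakes. The trial is still meant to inform dose and regimen, which relies on estimates from arms of six.

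**Conclusion.** The point holds. Under SAP 6.1.3, no GLI1 sample from an ET visit on Days 1–81 enters the primary analysis, by one of three rules, and no imputation brings it back. The analysis presented as ITT is a Week 12 observed-case analysis, and setting it beside Per Protocol does not show the effect of dropout on GLI1.

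A reader might go further and call it a completers' analysis. That is inexact: an ET visit on Days 82–88 counts, and so does a subject who stops drug but attends the scheduled Week 12 visit.

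The cost in precision is moderate for a single regimen (6.5% or 15.5% for one or two losses) and small for the combined contrast (0.7% or 1.5%). These figures assume one tumor per subject, whereas the planned analysis is by tumor with one or two each. Any bias depends on who leaves and cannot be sized from the documents. The change is worth making because it is cheap and the discarded data may be related to outcome; it is not a fatal flaw in an exploratory trial.

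**What to change.** 1. Keep the Week 12 GLI1 analysis and label it observed-case in SAP 6.7.1 and Table 14.2.1.1.
2. In SAP 6.1.3 and 6.7.1, exempt the end-of-treatment excision sample from visit windowing.
3. Add an ITT ANCOVA with the same model that uses the Week 12 or ET excision value whatever its study day, reported beside the Week-12-only result.
4. List days on drug and days since last application for each sample.

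A related text needs reconciling. The protocol synopsis allows excision within 14 days of Week 12, while Table 1 footnote h says 48 hours. If a late excision were recorded as an unscheduled visit on Day 89 or later, the same windowing rules would drop it.

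The cost is SAP wording, one added listing and one more model run on tissue already collected; no study procedure changes. The drawback is that some values in the added analysis reflect less than 12 weeks of treatment. The Week-12-only result and the listing of exposure make that visible.

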6.1.4 Adjustments for Covariates

Treatment group as factor and baseline values as covariate will be included in the primary and secondary endpoints analyses.

6.1.5 Handling of Dropouts or Missing Data

If a partial date is recorded for an adverse event start or end date, the following procedure will be followed. Other missing safety data dates will not be imputed.

If a partial date is reported where the day is missing, then the day will be imputed as the first day of the month unless the month is the same month as the first dose in which case the day will be that of first dose with the month and year remaining the same. If a partial date is reported where the month is missing, then the month will be imputed to January unless the year is the same year as the first dose in which case the month will be that of first dose with the year remaining the same. If a partial date where both the day and month is missing, follow details as stated previously.

Missing data post-Baseline through Week 12 will be imputed using last observation carried forward (LOCF) for the secondary endpoint of tumor size as assessed by the investigator. Specifically, if a single diameter is missing then that SEB's previous measurement will be carried forward. The analysis will also be performed without imputation of missing data. For the secondary endpoint of GLI1, no missing data will be imputed.

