9.1 Schedule of Evaluations and Procedures

9.1.1 Screening Visit (Day -42 to Day 0)

Following virtual electronic informed consent from each subject, the Investigator will determine whether subjects are eligible to participate in the study by performing screening tests and evaluations.

At the Screening visit, continuous monitoring of current and concomitant medications and therapies (including prophylactic treatments and medical interventions) and AEs throughout the study period will begin.

Screen failure information will be maintained at the site to document specified information, including but not limited to, reason for failure.

The following procedures will be conducted at this visit:

- 1. Obtain informed consent from the subject prior to performing any study related procedures. The subject will receive a copy of their signed consent form.
- 2. Review and explain the nature of the study and what will be expected at each visit to ensure subject can meet the requirements and has adequate transportation.
- 3. Assign the subject a 5-digit subject number, which will consist of the 2-digit site number and the 3-digit chronological screening order number, starting with 001 (e.g., 01 001, 01 002).
- 4. Record the subject's demographic information.
- 5. Record the subject's medical history.
- 6. Record all medications for BCC used during the prior year in the eCRF. Include all medications used in the past 30 days and any therapy that requires a washout prior to Baseline.
- 7. Record any prescription or over-the-counter therapies that are being used concomitantly in the eCRF.
- 8. The Investigator will identify 1 or 2 previously untreated non central facial BCCs
- 9. Verify that the subject meets the applicable inclusion/exclusion criteria as outlined in Sections 6.1 and 6.2.
- 10. Discuss the use of moisturizers and emollients with the subject.
- 11. Obtain a biopsy from the baseline treatment targeted BCC(s).
- 12. Collect blood samples for routine laboratory analysis [complete blood count/differential (CBC/Diff), urinalysis, serum chemistry and serum pregnancy test for females].
- 13. Record any AEs related to screening procedures on the AE eCRF.
- 14. Schedule subject's Baseline/Day 1 visit. If the subject requires a washout, schedule the Baseline/Day 1 visit to occur after the washout is complete.

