9.3.5.2 Documenting Adverse Events

It is the responsibility of the Investigator to document all AEs that occur during the course of the study. The AEs should be documented as a single medical diagnosis. When this is not possible, the AE should be documented in terms of signs and/or symptoms observed by the Investigator or reported by the subject at each study visit.

All AEs occurring after the subject signs the informed consent through the last study visit must be reported, regardless of whether or not the AEs are considered drug-related. All AEs, whether in response to a query, observed by the study site personnel, or reported spontaneously by the subject, will be recorded.

At each visit during the study, the subject will be assessed for the occurrence of new and ongoing AEs. Dermal safety and tolerability that result in the subject's requiring a concomitant therapy or discontinuation from the study will be reported as an AE. The following data will be collected on all AEs and recorded on the appropriate CRF:

- Event name (diagnosis preferred, if unknown, record the signs/symptoms)
- Onset date and end date
- Maximum intensity (severity)
- Seriousness
- Action taken regarding study drug
- Corrective treatment, if given
- Outcome

In addition, the Investigator's assessment of causality will be recorded.

Vital sign abnormalities are to be recorded as AEs only if they are clinically significant (for example: are symptomatic, requiring corrective treatment, leading to discontinuation or fulfilling a seriousness criterion).

Subjects will be questioned about any concurrent illness or systemic sign or symptom including but not limited to fatigue, loss or change in taste, nausea, vomiting, alopecia, diarrhea, and muscle spasms. Any incidence of these systemic signs or symptoms will be reported on the AE eCRF.

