6.8.2 Adverse Events

All AEs that occur during the study will be recorded and classified on the basis of Medical Dictionary for Regulatory Activities (MedDRA) terminology. Treatment-emergent Aes (TEAEs) are defined as Aes with an onset on or after the date of the first study drug application. Adverse events noted prior to the first study drug administration that worsen after Baseline will also be reported as Aes and included in the summaries.

Treatment-emergent Aes will be summarized by treatment group, the number of subjects reporting a TEAE, SOC, preferred term, severity, relationship to study drug (causality), and seriousness. When summarizing Aes by severity and relationship, each subject will be counted once within a system organ class or a preferred term by using the event with the highest severity and greatest relationship within each classification.

If relationship to study drug is reported as unknown, possible, probable or definite, then this is defined as related. If relationship to study drug is reported as unlikely or not related, then this is defined as unrelated.

Serious Aes will be summarized by treatment group, severity and relationship to study drug.

Listings will be presented for all adverse events as well as for serious adverse events and adverse events leading to study drug withdrawal.

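### The partial-date rule for adverse events in SAP 6.1.5 never checks one date against the other, so an end can precede its onset and an event over before dosing can count as treatment-emergent

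*SAP*

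**What the plan says.** SAP 6.1.5 is the only instruction for incomplete adverse-event dates; SAP 6.1 otherwise rules out imputing safety data. It begins: "If a partial date is recorded for an adverse event start or end date, the following procedure will be followed". The steps are:

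- Day missing: "the day will be imputed as the first day of the month unless the month is the same month as the first dose"; there, the first-dose day is used.
- Month missing: "the month will be imputed to January unless the year is the same year as the first dose"; in that year it becomes the first-dose month.
- Both missing: "If a partial date where both the day and month is missing, follow details as stated previously".

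The section has no separate rule for ends, no condition that an end fall on or after its onset, and no instruction to look at a recorded end before placing a start.

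SAP 6.8.2 then sets treatment-emergent status from onset alone: "Treatment-emergent Aes (TEAEs) are defined as Aes with an onset on or after the date of the first study drug application". It also brings in earlier events that worsen after Baseline, but that does not concern events already over.

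Pre-dose events will be in the database. Protocol 9.3.5.2 says: "All AEs occurring after the subject signs the informed consent through the last study visit must be reported". Protocol 9.1.1 lets screening start 42 days before dosing.

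**The concern.** First-of-month is a start-date convention. It moves a date early, and its first-dose exception leans towards counting an ambiguous event as on-treatment. For a start about which nothing else is known, that is cautious. For an end date, moving early is the wrong direction and can give an impossible sequence. For a start whose end is recorded as before dosing, the exception overrides what the record shows.

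Treatment-emergent status decides which events enter the adverse-event tables, and safety is the first primary objective. Groups are small. Under SAP 6.1.6 limited safety results also go to an unblinded sponsor after Cohorts 1 and 2 and again after Cohort 3, so the flag may be used before the trial ends. The SAP does not say in words that imputed starts feed the flag, but it describes no other use for them.

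**Working it through.** The documents state no figure on this point, so there is none to reproduce. The rule was applied literally.

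**Rule.** Let the first dose be on day dF of month mF in year yF. For a partial date in year y:

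- month m = recorded month; if missing, mF when y = yF, otherwise January;
- day d = recorded day; if missing, dF when (y, m) = (yF, mF), otherwise 1.

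**Worked dates, first dose 20 March 2017.**

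| Recorded | Imputed | Result |
|---|---|---|
| Onset 10 April, end April | end 1 April | 9 days before onset |
| Onset 25 March, end March | end 20 March | 5 days before onset |
| Onset 10 May, end 2017 | end 20 March | 51 days before onset |
| Onset 28 April, end May | end 1 May | no inversion |
| Start March, end 12 March | start 20 March | TEAE, starting 8 days after it ended |
| Start 2017, end 15 February | start 20 March | TEAE, starting 33 days after it ended |

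**Fault (a), end dates.** Take every first-dose date in a 365-day year and onset on each of Days 1 to 85, with the end in the onset month and its day missing: 365 × 85 = 31,025 cases. The imputed end is not before onset only when onset is on Day 1 (365 cases) or on the 1st of a later month (12 × 84 = 1,008 cases). So 31,025 − 365 − 1,008 = 29,652 invert, and 29,652 / 31,025 = 95.6%.

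The next figures drop the same-month condition and use onset on Days 1 to 99 with fixed durations that count the onset day. With the end day missing, the end falls before onset in 96%, 89%, 76%, 53% and 8% of events lasting 1, 3, 7, 14 and 28 days. Among those that end in their onset month, the share runs from 96% at 1 day to 70% at 28 days; only 11% of 28-day events fit inside one month. With end day and month both missing, it is 99%, 97% and 91% for 1, 7 and 28 days.

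**Fault (b), start dates.** Take onset on each of the 42 days before first dose, duration L, event over before dosing, start day missing and end known. The event becomes treatment-emergent when its onset is in the first-dose month. With n days in a month:

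share = Σ over 12 months of (n − L)(n − L + 1)/2, divided by 365 × (43 − L).

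| L (days) | Relabelled | Cases | Share |
|---|---|---|---|
| 1 | 5,373 | 365 × 42 = 15,330 | 35% |
| 3 | 4,679 | 365 × 40 = 14,600 | 32% |
| 7 | 3,435 | 365 × 36 = 13,140 | 26% |
| 14 | 1,720 | 365 × 29 = 10,585 | 16% |

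With start day and month both missing, enumeration gives 92% to 94%.

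**Size per subject.** Each cohort has 6 active subjects: 1/6 = 16.7 points. Pooled vehicle is 4 × 3 = 12: 1/12 = 8.3 points.

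**Does the repair work?** With the end set to the last day of its month, 0 of 180,675 cases (365 × 99 × 5 durations) invert. With the start capped at a known end, 0 of 53,655 (365 × (42 + 40 + 36 + 29)) are relabelled. Changing the end-date rule alone leaves fault (b) untouched, because the flag uses onset only.

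**The case against.** The strongest reply is that this is a small drafting gap. Onset and end dates are required adverse-event fields (Protocol 9.3.5.2), events are reviewed at each visit, and all data are source verified (Protocol 11.1), so partial dates may be few. No p-values are planned for adverse events, and every event is listed for about 36 subjects. The 17- and 8-point shifts need a misclassification to occur in a subject not already counted at that level. All of this stands and limits the weight of the point.

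Four stronger readings are tempting and are not supported:

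- *A reader might take 95.6% as a rate of TEAE error.* It concerns end dates only, under a same-month condition. The planned adverse-event tables use neither end date nor duration.
- *A reader might infer that sharing one rule between starts and ends creates the false TEAEs.* It does not. They come from the start-date part ignoring a known end.
- *A reader might infer that biopsy-site events will be turned into application-site reactions.* A screening biopsy happens at a dated visit, so its events are unlikely to lack an onset day. Inclusion criterion 5 also allows biopsy before screening, possibly before collection begins. Local tolerability is graded separately at visits and does not use these dates.
- *A reader might add that events are lost when the day is known but the month is not.* Day 5 with first dose on 20 March would indeed become 5 March, before dosing. That pattern is unusual and carries no weight here.

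Setting a partial start to first dose also remains a sensible cautious choice when the end is unknown or falls after dosing.

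**Conclusion.** The rule is wrong as written, in two independent ways. Read literally, it gives impossible end dates in nearly all cases where onset and end share a month and the end day is missing, and usually where the end month is missing too. An event that runs into a later month with only the end day missing is not inverted. The effect is confined to listings and any duration derived from them.

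Separately, the rule can label an event as treatment-emergent although its recorded end precedes the first dose. That does reach the summary tables, by about 17 points per affected subject in an active arm or 8 in pooled vehicle, provided the subject has no other TEAE at that level.

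The percentages assume equally likely calendar dates and are conditional on a date being partial. The documents give no frequency for that, so no expected number of affected subjects can be stated. It is worth correcting because the correction costs almost nothing, not because a large distortion has been shown.

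**What to change.** Replace the single procedure in SAP 6.1.5 with two.

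- **Start date.** Keep the present rule, with one exception. If the end date, known or partial, shows that the event ended before first dose, impute a start no later than that end and classify the event as not treatment-emergent. If the month is missing, treat the day as missing too.
- **End date.** Impute the last day of the recorded month, or 31 December if only the year is known, and never earlier than the start date. Apply any cap at last contact only where it does not contradict the recorded end month or year. Protocol 9.3.5.6 has events followed to resolution or stabilization, and serious events possibly beyond the subject's exit, so an unconditional cap could overwrite real data.

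Both parts are needed, since neither cures the other fault. The cost is a few lines of SAP text and one programming macro, with no new data. It is best done before the first unblinded safety report under SAP 6.1.6.
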